1.3.5. Efficacy, Pharmacokinetic, and Safety Parameters

Unless specified otherwise, all the efficacy endpoints will be defined and analyzed per RGDO cohort.

The primary endpoint is the proportion of patients in each subgroup of RGDO who achieve at least 5% body weight reduction from baseline at ~3 months treatment with setmelanotide.

The following 4 endpoints have been identified as secondary endpoints:

- Safety and tolerability of setmelanotide injection, assessed by the frequency and severity of AEs, vital signs, and laboratory evaluations.
- Change and percentage change from baseline in body weight.
- Change from baseline in Daily and Global Hunger Scores.
- Change from baseline in waist circumference.

2. ANALYSIS POPULATION

2.1. Population Definitions

The following analysis populations will be evaluated and used for presentation and analysis of the data:

- Safety Analysis (SA) Set: All patients who received at least 1 dose of study drug, excluding patients from Axis Sites #22 through #27 inclusive.
- Full Analysis Set (FAS): All patients who received at least 1 dose of study drug and have baseline weight data, excluding patients from Axis Sites #22 through #27 inclusive.
- Completer's Set (CS): All patients in the FAS who have non-missing weight data collected at least once between 60 days and 120 days on therapeutic dose, inclusive.
 - For patients enrolled prior to amendment 9, therapeutic dose will be considered the maximum dose received during the dose escalation phase (identified by Clinical Visit 2X). For patients enrolled post-amendment 9, the therapeutic dose will be considered the dose received at Visit 3.
 - The first date that this dose was received will be considered the date of the first therapeutic dose (this will be the date of Visit 3 for post-amendment 9 patients). If a patient has a visit falling within 60 to 120 days after first therapeutic dose and was still on treatment, this visit should be considered for analysis as ~3 months of treatment. If a patient has two visits falling within this window, the visit closest to Day 90 in which the patient was still on treatment should be considered. If a patient has two visits falling within this window that are equidistant from Day 90, the later visit should be considered. For post-amendment 9 patients, if the patient's last visit during the study is Study Visit 5 and the patient is still on treatment, then that date should be used for this analysis, even if it does not fall within 60 to 120 days after first therapeutic dose. If a patient has no visit falling within this window, this patient will be treated as missing for completer's analysis purposes. If a patient has no visit falling within this window and no observation prior to the window, this patient will be treated as missing for analysis purposes, as well.
- Per-Protocol (PP) Set: All patients in the FAS without any major protocol violations.

The FAS is the primary population for the analysis of efficacy parameters. Sensitivity analyses of efficacy parameters may be conducted on the CS population, if appropriate. A subset of efficacy parameters may be evaluated for the PP Set if the population in PP is over 20% different from the FAS population. The SA Set is the primary population for the analysis of PK parameters and safety endpoints.

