4.2. Demographics and Baseline Characteristics

Demographics and baseline characteristics will be summarized and presented by subgroup of RGDO and overall. Age at enrollment, height at baseline, weight at baseline, waist circumference at baseline, and BMI at baseline will be summarized using descriptive statistics (N, mean, SD, 90% CI of the mean, median, minimum, and maximum). The number and percentage of patients in each sex, ethnicity, race, baseline Fitzpatrick classification, and genetic deficiency categories will be presented. The number and percentage of patients with cognitive impairment will also be presented. No formal statistical comparisons will be performed. Patient demographics will include patients in the FAS.

4.3. All Medical History events will be coded using the MedDRA coding system and displayed in tables by RGDO and overall, and in data listings using system organ class and preferred term. Efficacy Analyses

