4.3.1. Primary Analysis

The primary analysis on the primary endpoint will be based on the FAS.

The primary endpoint is the proportion of patients in each subgroup of RGDO who achieve at least 5% reduction from baseline in body weight (i.e., are 'responders') after ~3 months of treatment with setmelanotide.

The visit designated for analysis at ~3 months of treatment will be identified as follows: A patient's therapeutic dose will first be established. For patients enrolled prior to amendment 9, therapeutic dose will be considered the max dose received during the dose escalation phase (identified by Clinical Visit 2X). For patients enrolled post-amendment 9, the therapeutic dose will be considered the dose received at Visit 3. The first date that this dose was received will be considered the date of the first therapeutic dose (this will be the date of Visit 3 for post-amendment 9 patients). If a patient has a visit falling within 60 to 120 days after first therapeutic dose, this visit should be considered for analysis as ~3 months of treatment. If a patient has two visits falling within this window, the visit closest to Day 90 should be considered. If a patient has two visits falling within this window that are equidistant from Day 90, the later visit should be considered. If a patient has no visit falling within this window, the last observation before the window will be used for analysis purposes. If a patient has no visit falling within this window and no observation prior to the window, this patient will be treated as missing for analysis purposes.

The summary of the primary endpoint and the associated two-sided 90% Clopper-Pearson

confidence interval will be provided. Descriptive statistics for the actual, change, and percent change from baseline in body weight (kg) at the ~3 month analysis endpoint will be presented for patients of the FAS by RGDO.

Body weight (kg) will be recorded as shown in the SOA ([Table 1-1](#), [Table 1-2](#), [Table 1-3](#), and [Table 2](#)). Weight is repeated in triplicate and the mean weight is calculated per study visit. Mean weight will be utilized for analysis purposes.

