4.6. Safety Analyses

Safety analyses will be conducted using the SA Set.

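### SAP 2.1 removes six undefined 'Axis' sites from the Safety Analysis Set and the FAS without a visible reason, so anyone dosed there is in no safety incidence table and no primary responder proportion

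*SAP*

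**What the plan says.** SAP 2.1 defines four analysis sets.

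- SA Set: "Safety Analysis (SA) Set: All patients who received at least 1 dose of study drug, excluding patients from Axis Sites #22 through #27 inclusive".
- FAS: dosed patients who "have baseline weight data, excluding patients from Axis Sites #22 through #27 inclusive".
- Completer's Set: "All patients in the FAS who have non-missing weight data" in a stated time window.
- Per-Protocol Set: "All patients in the FAS without any major protocol violations".

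The sets are then assigned to analyses. SAP 2.1 states: "The SA Set is the primary population for the analysis of PK parameters and safety endpoints". SAP 4.6 repeats it: "Safety analyses will be conducted using the SA Set". SAP 4.3.1 states: "The primary analysis on the primary endpoint will be based on the FAS". SAP 4.2 adds: "Patient demographics will include patients in the FAS".

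The term for the six sites occurs only in these two definitions. Protocol 8.4 describes a 3-digit site number and no separate Axis numbering, so the supplied text does not show which sites are meant.

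**The concern.** A safety set is normally fixed by exposure: whoever was dosed is counted. Here exposure is the starting point, and six sites are then taken out by number. Safety and tolerability, assessed partly by adverse event frequency, is the first-listed secondary endpoint (SAP 1.3.5). An adverse event, SAE or death in a patient dosed at one of these sites would add to neither the numerator nor the denominator of any planned incidence.

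The clause also works outside the SAP's own route for problem data. SAP 2.2 provides a violation file, finalized before database lock, which can remove patients only from the Per-Protocol Set. The site clause acts on the two main sets with no reason or decision date in view. The study is open-label and the sponsor sees all data in real time (Protocol 7.5), so a reader needs the reason and date to confirm that the choice did not depend on outcomes. The gap alone does not suggest that it did.

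**Working it through.** **1. Which set holds these patients?** The SA Set and the FAS exclude them by name. The Completer's Set and the Per-Protocol Set are subsets of the FAS and inherit the exclusion. No named analysis set contains them.

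**2. What still covers them?**

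- SAP 4.1 tabulates the number treated and the size of each population for all screened patients. Number treated minus SA Set gives the total excluded, but a count by genetic subgroup is not promised.
- SAP 3.10 lists all case report form data, and SAP 4.6.1 lists all on-study adverse events. SAP 4.6 does not say whether its listings are limited to the SA Set.
- SAE reporting (Protocol 12.2) and data safety monitoring board review (Protocol 7.5) state no site exclusion.

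None of these gives an incidence.

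**3. How many patients?** The documents give no count k, and k may be 0. For illustration only, assume that the six site numbers (27 - 22 + 1 = 6) are among the planned 50 to 75 sites (Protocol Synopsis) and that about 150 patients (Protocol 8.1) enrol evenly:

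- 75 sites: 150 x 6/75 = 12 (8%), leaving 138.
- 50 sites: 150 x 6/50 = 18 (12%), leaving 132.

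**4. Chance that an event vanishes from the tables.** This needs no event among the retained patients and at least one among the excluded. With incidence p, independent patients and no dependence on site:

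P = (1-p)^(150-k) x [1 - (1-p)^k] = (1-p)^(150-k) - (1-p)^150

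| p (assumed) | k = 12 | k = 18 |
|---|---|---|
| 1% | 0.24984 - 0.22145 = 2.8% | 0.26537 - 0.22145 = 4.4% |
| 5% | 0.04% | 0.07% |

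At p = 1% the chance is 0.2% for k = 1 and 1.4% for k = 6. At k = 0 it is zero.

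**5. Loss of precision.** With no events among N patients, the one-sided 95% upper bound is 1 - 0.05^(1/N): 1.98% at N = 150, 2.15% at 138 and 2.24% at 132.

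**6. Primary endpoint.** Take one patient out of a subgroup of n with r responders. Removing a responder shifts the proportion by (n-r)/(n(n-1)); removing a non-responder shifts it by r/(n(n-1)). Over all r the shift lies between 0 and 1/n: up to 20 points at n = 5 and up to 6.7 points at n = 15. With the two-sided 90% Clopper-Pearson interval of SAP 4.3.1 and assumed counts:

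- 0/5 (0-45.1%) becomes 0/4 (0-52.7%): same estimate, wider interval.
- 2/5 = 40% (7.6-81.1%) becomes 1/4 = 25% (1.3-75.1%) or 2/4 = 50% (9.8-90.2%).

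**The case against.** The strongest reply is that the clause may do nothing. No count is given, the site numbering is not tied to this protocol's site numbers, and even enrolment is only a convenience in so rare a population. A reason may also be recorded in text that was removed or redacted, although the definitions themselves show no redaction. If that reason is unreliable data, keeping these patients out of the main tables could be defensible. All of this stands. It limits the size of the point and makes the fix conditional, but it does not put any dosed patient into an incidence table.

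A reader might infer more than the documents support:

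- **That the exclusion contradicts the protocol.** Protocol 13.4 says all collected data enter the endpoint analyses, but that sentence concerns retaining patients and out-of-window data. The same section leaves populations to the SAP, and SAP 1.1.1 gives the SAP precedence.
- **That events at these sites escape oversight.** SAE reporting and board review carry no site limit. The gap is in the summary tables.
- **That a safety signal would probably be lost.** With 12 to 18 excluded, the chance that at least one affected patient is among them is 11.4-16.5% for a 1% event and 46.0-60.3% for a 5% event. That is not the chance of losing the event. At 5%, about 6.6 to 6.9 affected patients are expected among the 132 to 138 retained, so the event would almost surely still appear.

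**Conclusion.** The point holds for the plan as written, and its size is unknown. Any patient dosed at the six sites is outside every SAP 4.6 incidence table and every primary responder proportion, and the supplied text gives no definition or reason.

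Under the even-enrolment illustration, the chance of losing an event entirely is 2.8-4.4% at 1% incidence and under 0.1% at 5%, and the loss of precision is small. These figures assume that risk does not depend on site, in which case the percentages are not biased. If risk or reporting does differ at these sites, the tables could be biased by an amount the documents cannot bound. Without a stated reason a reader cannot tell which case applies.

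The safety set should be corrected. The FAS part is minor: results are descriptive (SAP 3.1 and 3.7), and what is missing is mainly documentation, although one patient can move a small subgroup's proportion visibly.

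**What to change.** **Safety set.** Define the SA Set in SAP 2.1 by exposure alone: every patient given one or more doses. Present the adverse event, SAE and death tables with and without these sites, provided their data are in the study database. If the data are not there, or if a documented data-reliability reason keeps the exclusion, report separately the number treated at these sites and their adverse events, SAEs and deaths. State in SAP 4.6 that the corresponding listings cover all treated patients.

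**FAS (minor).** Define the term, state the reason and the decision date, and report the primary endpoint with and without these sites.

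**If nobody was dosed there,** say so and delete the clause from both definitions.

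**Cost.** A wording change in the SAP and one extra run of the safety and primary tables. The documents do not confirm that these sites' data are available. The downside is that the main safety tables may carry less reliable data; the tables without these sites make that visible.

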- 6 The Dose Titration phase will be a variable schedule lasting a minimum of 2 weeks in which patients will return to the clinic approximately every 2 weeks in order to establish the individual patient's therapeutic dose according to Protocol. Given the variable number of dose titration steps in the Dose Titration Phase, each Dose Titration Visit Number (V) will remain V2 with an alphabetized suffix added to each titration visit (i.e.; first dose titration at start of Week 1 = V2a, second dose titration at start of Week 3 = V2b, etc.). This will allow for the Visits to be appropriately tracked. Additionally, each dose titration visit will have the same pre and post dose assessments as outlined in the SOA (with the exception of Anti-Rm-493 antibodies, metabolic and hormonal assays, ECG, Inclusion/Exclusion review and Medical History Review).
- 7 Once the patient's individual therapeutic dose is established the patient will enter the Open Label Active Treatment phase for 10 additional weeks, for a combined total of 12 weeks of dosing at the therapeutic dose. During this time, the study calendar will be reset, starting when the therapeutic dose was initiated (i.e. the last 2 weeks of dose titration when the therapeutic dose was established). Therefore, the Open Label Active Treatment phase starts at the beginning of Week 3 (V2x – final dose titration visit). Patients losing 5 kg of weight (or 5% if baseline weight is < 100 kg) at the end of the Open Label Treatment phase will be eligible to enter the one-year extension.
- 8 During the titration period and the 10-week Open Label Treatment Period, patients (and/or parents/guardians) will measure blood pressure and heart rate at home once daily prior to dosing in the morning, and record the values. The measurements should be taken in triplicate and all 3 readings recorded. If needed, Rhythm will supply a blood pressure machine for these readings.

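### Completer's Set: the Visit 5 exception depends on Visit 5 being the last visit attended, so post-Amendment 9 patients with the same on-drug Visit 5 weight can be classified oppositely

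*SAP*

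**What the plan says.** SAP 2.1 admits to the Completer's Set those FAS patients who have "non-missing weight data collected at least once between 60 days and 120 days on therapeutic dose, inclusive". A visit is eligible as the ~3-month visit on this condition: "If a patient has a visit falling within 60 to 120 days after first therapeutic dose and was still on treatment". The clock starts when the therapeutic dose was first received, and the SAP adds in brackets that "this will be the date of Visit 3 for post-amendment 9 patients".

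There is one exception, for post-Amendment 9 patients: "if the patient's last visit during the study is Study Visit 5 and the patient is still on treatment", the date of that visit is used, "even if it does not fall within 60 to 120 days after first therapeutic dose". For the rest: "If a patient has no visit falling within this window, this patient will be treated as missing for completer's analysis purposes". The exception is not offered to patients enrolled before Amendment 9. The SAP does not say whether a Treatment Discontinuation Visit or Visit 7 counts as the last visit.

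The same section makes the FAS the primary efficacy population and leaves analyses on the Completer's Set optional. SAP 4.3.1 gives the FAS rule. It uses the same window but has no on-treatment condition and no Visit 5 exception, and it falls back on the last observation before the window.

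**The concern.** There are two problems in the definition.

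- **The lead sentence and the exception do not agree.** The lead sentence makes a weight at 60 to 120 days a condition of membership. The exception supplies a weight from outside that range without amending the condition. One programmer could exclude these patients and another include them.
- **The trigger is attendance, not treatment.** What makes the Visit 5 weight usable is that the patient was not seen again. Protocol 12.2.4 encourages patients withdrawn for an adverse event to attend a final or early termination visit, and Protocol Table 3 schedules a weight at the Treatment Discontinuation Visit and at Visit 7. A patient who does this off drug can lose a place in the set that a patient who simply disappears would keep.

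The Completer's Set is the only efficacy set defined with an on-treatment condition, so its membership ought to follow treatment received. Suppose the off-drug return falls inside the window. SAP 4.3.1 then takes that off-drug weight for the FAS, and the Completer's Set counts the patient as missing. The on-drug Visit 5 weight enters neither ~3-month responder summary. Protocol 8.1 expects cohorts of 1 to 15, so one patient is visible in the result.

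**Working it through.** **Inputs.** From SAP Table 2: Visit 3 on Day 29, Visit 5 on Day 85, Visit 6 on Day 113, Visit 7 on Day 141, each ±3 days. From SAP 1.3.1: patients aged 16 and over start 3.0 mg on Day 15. From SAP 2.1: window 60 to 120 days, clock from Visit 3.

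**Check of the calendar.** SAP 1.3.1 states 12 weeks at 3.0 mg for patients aged 6 up to 16, and 14 weeks for older patients. (113 − 29)/7 = 12.0 and (113 − 15)/7 = 14.0, so both are reproduced.

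**Where the visits fall, clock from Visit 3.**
- Visit 5: 85 − 29 = 56 days, outside the window. With ±3 days at each visit the range is 82 − 32 = 50 to 88 − 26 = 62. Of the 49 day combinations, 6 reach day 60 or later; reading that as a share (12%) assumes independent, uniform deviations.
- Visit 6: 113 − 29 = 84 days, inside.
- Visit 7: 141 − 29 = 112 days, inside by date, but it fails the on-treatment condition if the patient is off drug.

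**The rule applied literally** to post-Amendment 9 patients with an on-drug Visit 5 weight at 56 days:

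| After Visit 5 | Completer's Set |
|---|---|
| Never seen again | In, by the exception |
| Discontinuation visit off drug, e.g. day 70 | Missing |
| Visit 7 off drug | Missing |
| Discontinuation visit before day 60, even on drug | Missing |
| Visit at day 60 to 120 still on drug | In, by the ordinary window |

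The first three rows have the same usable on-drug weight and different status.

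**The other reading of the clock.** If day 0 is when 3.0 mg was first received, a patient aged 16 or over reaches Visit 5 at 85 − 15 = 70 days. That is inside the window, and no exception is needed.

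**Size.** A patient who is missing leaves the denominator as well. With k responders out of n, losing a responder changes the rate by k/n − (k−1)/(n−1) = (n−k)/[n(n−1)]. Losing a non-responder changes it by k/(n−1) − k/n = k/[n(n−1)]. Either is at most 1/n. For n = 5, with assumed counts and two-sided 90% Clopper-Pearson intervals:
- 3/5 = 60% (18.9 to 92.4)
- non-responder lost: 3/4 = 75% (24.9 to 98.7), a change of 3/20 = 15 points
- responder lost: 2/4 = 50% (9.8 to 90.2), a change of 2/20 = 10 points
- extremes: 1/5 to 0/4, or 4/5 to 4/4, a change of 20 points

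**The case against.** The strongest reply is that little depends on this. SAP 2.1 only allows for analyses on the Completer's Set where appropriate, the study is descriptive, and the primary FAS analysis never uses the exception. With no visit in the window, the FAS takes the last earlier observation, which is the Visit 5 weight when no later weight precedes the window. This stands, and it limits the point to a sensitivity analysis.

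It can also be said that the exception is an express carve-out, not a contradiction. That is fair as to intent. The lead sentence still needs to say so.

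The opposite classification assumes that a discontinuation visit counts as the last visit, which the SAP leaves undefined, and the documents do not fix that visit's timing relative to the last dose. This stands in part. Even if the discontinuation visit were not counted, Visit 7 is a numbered study visit, and an off-drug Visit 7 gives the same result.

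The 56 days is firm for patients under 16. For older patients it rests on the Visit 3 anchor.

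A reader might infer two stronger points, and the documents support neither.
- **That the exception treats the enrolment eras unequally at equal exposure.** Before Amendment 9, "the study calendar will be reset, starting when the therapeutic dose was initiated" (SAP Tables 1-1 to 1-3, footnote 7). That schedule's Visit 5, on Day 57, is therefore also 57 − 1 = 56 days on therapeutic dose. Total exposure differs, however. Post-Amendment 9 Visit 5 is 85 − 1 = 84 days after first dose. Titration before Amendment 9 could be a single two-week step, already counted in the reset calendar, so total exposure there can be as short as 56 days. The endpoint is framed as about 3 months of treatment, so the restriction tracks a real difference.
- **That the rule systematically favours unexplained losses over documented stops, and so biases the result.** The documents give no dropout figures or outcomes by reason for leaving, so the direction cannot be known.

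**Conclusion.** The point holds for post-Amendment 9 patients. As written, whether an on-drug Visit 5 weight counts depends on whether the patient was seen again, and the lead sentence does not accommodate the exception. It should be corrected, but it is confined to an optional sensitivity set and leaves the primary responder analysis as it is. In a cohort of five, one patient typically moves the completer rate by 10 to 15 points and at most by 20. The number of patients affected is unknown.

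The conclusion assumes the SAP's Visit 3 anchor, nominal visit days, a literal reading of the last visit, and a later visit that is off drug or before day 60.

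**What to change.** Before database lock, in SAP 2.1:

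1. Replace "if the patient's last visit during the study is Study Visit 5 and the patient is still on treatment" with: *the patient's last on-treatment weight is at Study Visit 5*.
2. Add the exception to the lead sentence of the Completer's Set definition.
3. Report, by cohort, how many patients enter the set through the exception.
4. Reconcile the date the dose was first received with the Visit 3 anchor for patients aged 16 and over, and state one clock start.

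The new trigger settles the off-drug returns. A discontinuation weight taken on drug before day 60 would itself be the last on-treatment weight, so the text should also say whether such a patient is in or out. The exception should not be extended to patients enrolled before Amendment 9, given their possibly shorter total exposure.

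The cost is a few sentences and a small derivation change, with no new data. The downside is that a few patients who stopped drug after Visit 5 enter a sensitivity set. Protocol 7.5 gives the sponsor real-time access to all data in this open-label study, so settling the rule early keeps membership from being decided with responder status in view.
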